
I.4. PROCEDURAL FLOW-CHART

Study Visit	1	2	3	4	5	6	7	8	8'	9
	1-6 weeks prior to visit 2	Day 0	Day 4±1	Day 7±1	Day 11±1	Day 14±1	Day 21±1	Day 28 -1; +7	Day 45 -5; +10	Month 6±1
Administrative Requirements:										
Recruitment, Medical record number, Screen form, Information and study consent ^a	X									
Demographic information (age, gender, ethnicity)	X									
Vaccination:										
Clinical Requirements:										
Complete medical history	X									
Physical examination include vital signs ^b	X	X	X	X	X	X	X	X	X	X
Interim History/Diary (AEFI documentation, concomitant medication) ^{c,d}		X	X	X	X	X	X	X	X	X
Randomization		X								
Safety Labs:										
ECG	X									
Hematology ^e	X	X		X		X		X		X
Blood chemistry ^f	X									
Screening for HIV, hepatitis B and C ^g	X									
Serum pertussis toxin and pertactin IgG antibodies	X									
Urine analysis ^h	X	X*						X*		
Nasopharyngeal aspirate for BPZE1 culture and quantitative colony counts			X	X	X	X	X	X ⁱ	X ⁱ	
Immunogenicity Labs and Sample Archive:										
Binding pertussis serum antibodies		X		X		X	X	X		X
Binding pertussis nasopharyngeal antibodies			X	X		X	X	X		X
Nasopharyngeal cytokines			X	X	X	X	X	X		X
Lymphoproliferative response		X	X ^j			X		X		X
Cryo-preserved cells		X				X		X		X
TOTAL BLOOD VOLUME APPROXIMATELY (ML)	23	109	16 ^l	8.5		109	4.5	109		109

(a) The ICF must be signed by the subject and investigator before any study specific procedure.

(b) At Visit 1, full physical examination (e.g. inspection of tonsils, palpation of glands, auscultation of pulm, measuring height and weight) including ECG and vital signs (oral temperature, blood pressure, heart rate, respiratory rate). For the following visits, physical exam will be restricted to general appearance, heart, lung, skin, nose, throat and vital signs.

(c) Adverse events following immunization (AEFI) occurring within 2 hours post-vaccination have to be recorded at the study centre and AEFI occurring from Day 0 to Day 28 have to be recorded in the Diary. If a vaccine-related AEFI is not resolved by Day 28, it must be followed up until resolution or stabilization.

(d) Serious adverse events (SAE) occurring from Visit 1 (screening) to Visit 9 have to be recorded at the study site. If an SAE is not resolved at the last visit of the concerned subject, it must be followed up until resolution or stabilization.

(e) Hematology (haemoglobin, total and differential WBC, RBC, platelets).

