(f) Blood chemistry (potassium, calcium, sodium, creatinin, albumin, serum bilirubin, alkaline phosphatases, alaninaminotransferase (ALAT), aspartataminotransferase (ASAT), glutamyltransferase (GT), high sensitive C-reactive protein, blood glucose, thyroidea stimulating hormone (TSH), human chorionic gonadotropin (hCG), females only.

(g) Including HIV1/HIV2, HBsAg, anti-HBc and anti-HCV.

(h) Dipstick analysis of pH, erythrocytes, leucocytes, protein, glucose, ketones and bacteria (nitrite) and the drugs cocaine, amphetamine, cannabis, morphine, benzodiazepines, and methylenedioxymethamphetamine. *Urine dipstick pregnancy test is to be done at visit 2 before randomization (if positive exclude) and at visit 8.

(i) If positive culture after 4 weeks a new nasopharyngeal sample should be collected 2-4 weeks later for culture.

(j) Only high dose group 3.

II. Important medical procedures to be followed by the investigator

II.1. EYE EXPOSURE

The Principle Investigator (PI) or delegate at the clinical trial centre will see all staff and any volunteer who accidentally gets droplets of the vaccine in the eye. The principal investigator or delegate will see all non-trivial cases. Equipment for eye washing will be available. Protective goggles (included in universal precautions) will be worn by subject and staff when administering the vaccine.

Accidental exposure of health care staff should be reported according to the routine at the Karolinska Trial Alliance, Karolinska University Hospital.

II.2. STOPPING CRITERIA FOR DOSE ESCALATION/CONTINUATION OF STUDY

In this study adverse events following immunization (AEFI) are defined according to the current definition generally used in vaccine pharmacovigilance (Report of CIOMS/WHO Working Group on vaccine pharmacovigilance 2012) as: *"any untoward medical occurrence which follows immunization and which does not necessarily have a causal relationship with the usage of the vaccine. The adverse event may be any unfavourable or unintended sign, abnormal laboratory finding, symptom or disease."*

An AEFI is considered serious if it results in death, is life-threatening, requires in-patient hospitalization or prolongation of existing hospitalization, results in persistent or significant disability/incapacity, or is a congenital anomaly/birth defect.

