All SAE will be reported in due time by the investigator to the sponsor with copy to the trial PI. Then the PI or the sponsor will request a DSMB meeting. The DSMB should give advice to the sponsor about stopping the study (temporarily or permanently) or continuing the study. The following criteria will be considered:

- The study may be stopped if a volunteer within the period 0-28 days after vaccination suffers from clinical whooping cough without laboratory demonstration of wild-type *B. pertussis*. In such a case it must be suspected that the symptoms are caused by BPZE1.
- The study may be stopped if a volunteer has a SAE which is considered by the DSMB to be most probably caused by BPZE1.

II.3. METHOD OF BLINDING AND BREAKING THE STUDY BLIND

The 16 subjects in each dosage group study will be vaccinated in a double-blind manner (active vaccine vs. placebo). That means that all trial participants and all site staff involved in participant recruitment and follow-up will be blinded to treatment assignment. Vaccine and placebo are not distinguishable at the 10^7 dose level when thawed. For higher dose levels (10^8 , 10^9), where vaccine and placebo may be distinguishable when thawed, observer-blinding will be established, by the fact that the vaccine will be prepared and administered by a study nurse not involved in any other trial procedures

Sponsor staff and laboratory staff involved in review/analysis of data are unaware of the treatment assignments. The 6 volunteers with high PRN antibodies in the control group (group 4) will be vaccinated with active vaccine (no blinding, open label).

The information if a vial contains vaccine or placebo will only be available at the statistics center (EUCLID), Lund University Hospital pharmacy (for emergency unblinding), at the manufacturer's site (Q Biologicals) and at the sponsor pharmacovigilance site.

Since access to results of the cultivation of BPZE1 from the nasopharynx samples and the antibody determination may lead to treatment unblinding, these results will be strictly controlled within the respective laboratory. The access of these results outside the laboratory will be contingent on having a previous access to the randomization list and therefore will only be authorized after the completion of

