the study, with the exception a statistician in order to perform an interim analysis after 28-days follow-up. At the end of the trial, the study will be unblinded after all safety and laboratory results are monitored and the data bases are locked.

EXCEPTIONS!

- 1) If any subject has detectable vaccine strain bacteria in the nasopharyngeal sample collected 28 (-1; +7) days after vaccination. Under such a circumstance the laboratory has to inform the investigator, who should arrange for an extra visit for collection of a new nasopharyngeal sample for control of bacterial presence.
- 2) In case of a medical event that investigator/physician in charge of the participant feels cannot be treated without knowing the identity of the study treatment, an emergency unblinding procedure is in place at the Lund University Hospital pharmacy (available 24 hours 7 days a week). If there is a possibility the investigator or delegate should be contacted before the code is broken. The investigator/physician in charge sends a fax of request to the pharmacy, which breaks the code by opening the individual sealed envelope, fills in the unblinding form and faxes the completed form to the investigator/physician in charge. The sponsor should be informed within 24 hours of any unblinding. As far as possible all examinations during study follow-up must be performed on all subjects who received the investigational product.

Unblinded interim reports for the DSMB will be prepared before escalation to the next dose by the trial statistician. An additional interim analysis will be performed when culture results are available from twenty-eight days after vaccination of the high dose group 3. For the latter, another statistician will get access to the randomization list for groups 1-3 to provide a summary of safety and colonization data to the Sponsor/ILiAD for use in discussion with regulatory agencies about a Phase II study. The interim analysis will provide no information about individual volunteers that could reveal the vial codes and the statistician performing the interim analysis will not be involved in any other trial procedure or in the final statistical analyses.

III. Introduction

III.1. BACKGROUND

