B. pertussis has not been shown to be allergenic in any preclinical or clinical studies to date. On the contrary the BPZE1 has been demonstrated to protect against airway inflammations induced by allergens or viral infections in a mouse model. The BPZE1 has also been shown to protect against infection with wild type *B. pertussis* infection already 3 hours after immunization in a mouse model (Mielcarek et al., Live attenuated *B. pertussis* as a single-dose nasal vaccine against whooping cough. PLoS Pathog 2006;2:e65).

The BPZE1 vaccine or placebo will be administered nasally via tuberculin syringes to healthy adult volunteers under strictly controlled conditions at the Karolinska Trial Alliance phase I unit. To minimize the risk of transmission the volunteers will stay at the study centre for 6 hours after administration of the vaccine. In addition volunteers with frequent contact with infants below one year of age or individuals with immunodeficiency will be excluded from participation in the study. The attenuated BPZE1 bacteria colonize the upper respiratory tract similarly to the wild-type *B. pertussis*. Colonization of live organism will be followed in nasopharyngeal aspirates performed at various intervals from the day of administration until the end of the study. Chronic carriage of *B. pertussis* has not been reported and is therefore not expected.

To avoid accidental exposure actions should be taken to minimize generation of aerosols, since the bacteria is strictly a respiratory tract organism. The volunteers and the staff members should wear eye-protective glasses during the vaccination. Persons handling the BPZE1 bacteria should wear gloves and must wash their hands with a suitable disinfecting soap before touching their skin and eyes. Effective antibiotic treatment with e.g. erythromycin will be given in case of accidental transmission to other humans.

Female mice when vaccinated with BPZE1 shortly before mating showed no negative effect on their pregnancy nor on their offspring. As a matter of fact, the offspring were protected against *B. pertussis* challenge.

In summary, the risk assessment for this study shows a very low potential risk for the volunteers and impact associated with administering the BPZE1.

IV. Study objectives

IV.1. PRIMARY OBJECTIVE: SAFETY

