3. Collect blood samples as described in section XII.3. "*Blood samples*". Complete the appropriate document provided in the investigator or delegate Site file.
4. Collect nasopharyngeal aspirate as described in section XII.4. "*Nasopharyngeal samples*". Complete the appropriate document provided in the investigator or delegate Site file.
5. Arrange for an appointment for visit 8 (28 (-1; +7) days after visit 2)

VI.3.9. Visit 8, 28 (-1; +7) days after visit 2

During this visit the investigator or delegate will:

1. Collect and review the Diary. Check for any AEFI, interview on AR from the respiratory tract and systemic adverse events that might have occurred since visit 7, or any adverse event corresponding to the definition of a SAE (refer to Section XIII. "*Recording and reporting of adverse events*"), and check for any concomitant medication.
2. Perform a limited physical examination and measure blood pressure, heart rate, respiratory rate and record the information in the subject's CRF.
3. Collect blood samples as described in section XII.3. "*Blood samples*". Complete the appropriate document provided in the investigator or delegate Site file.
4. Collect nasopharyngeal aspirate as described in section XII.4. "*Nasopharyngeal samples*". Complete the appropriate document provided in the investigator or delegate Site file.
5. Collect urine sample from females and do a dip stick pregnancy testing.
6. Arrange for an appointment for visit 9 (6±1 months after visit 2).

VI.3.10. Visit 8', 45(-5; +10) days after visit 2

In case the nasopharyngeal aspirate contains detectable vaccine strain bacteria on day 28 the laboratory contacts the clinical investigator or delegate, who contacts the subject for a new visit.

During this visit the investigator or delegate will:

1. Collect information on any AEFI, interview on AR from the respiratory tract and systemic adverse events that might have occurred since visit 8, or any adverse event corresponding to the definition of a SAE (refer to Section XIII. "*Recording and reporting of adverse events*"), and check for any concomitant medication.
2. Perform a limited physical examination and measure blood pressure, heart rate, respiratory rate and record the information in the subject's CRF.
3. Collect nasopharyngeal aspirate as described in section XII.4. "*Nasopharyngeal samples*". Complete the appropriate document provided in the investigator or delegate Site file.

VI.3.11. Visit 9, 6±1months after visit 2

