Since access to results of the cultivation of BPZE1 from the nasopharynx samples and the antibody determination may lead to treatment unblinding, these results will be strictly controlled within the respective laboratory. The access of these results outside the laboratory will be contingent on having a previous access to the randomization list and therefore will only be authorized after the completion of the study, with the exception a statistician in order to perform an interim analysis after 28-days follow-up. At the end of the trial, the study will be unblinded after all safety and laboratory results from 6 months follow up are monitored and the data bases are locked. The volunteers will be blinded until after the 12 month-follow up.

Unblinded interim reports for the DSMB will be prepared before escalation to the next dose by the trial statistician. An additional interim analysis will be performed when culture results are available from twenty-eight days after vaccination of the high dose group 3 and 4, respectively. For the latter, another statistician will get access to the randomization list for groups 1-3 to provide a summary of safety and colonization data to the Sponsor/ILiAD for use in discussion with regulatory agencies about a Phase II study. The interim analysis will provide no information about individual volunteers that could reveal the vial codes and the statistician performing the interim analysis will not be involved in any other trial procedure or in the final statistical analyses.

A clinical study report containing data of the primary and secondary end-points will be prepared when the safety and laboratory results from 6 months follow up are monitored and the data bases are locked. A separate report will be prepared containing the results of the 12 months follow up.

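### Section III.3 says BPZE1 carriage is followed to study end, but culture stops at Visit 8 or 8', and a participant still positive at Visit 8' has no stated notification and no later culture

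*Combined protocol and SAP*

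**What the plan says.** **The assurance.** The volunteers' risk assessment in protocol III.3 says that colonization "will be followed in nasopharyngeal aspirates performed at various intervals from the day of administration until the end of the study". Section VI.1 sets the end of the trial at the final participant's final visit.

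**The schedule.** In the flow chart (I.4), the row "Nasopharyngeal aspirate for BPZE1 culture and quantitative colony counts" is marked at Visits 3 to 8 and at Visit 8'. The table in XII.4 agrees. The synopsis makes Visit 8' conditional on a positive Day-28 sample. At Visit 9 an aspirate is collected (VI.3.11), but the synopsis, flow chart and XII.4 assign it to immunological assays only.

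**The hold on results.** Section II.3 says of culture and antibody results that "these results will be strictly controlled within the respective laboratory". Release outside the laboratory waits for study completion, apart from a statistician for the interim analysis. SAP 1.4 repeats this: access "will only be authorized after the completion of the study, with the exception a statistician".

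**The exception.** Exception 1 in II.3 begins "If any subject has detectable vaccine strain bacteria in the nasopharyngeal sample collected 28 (-1; +7) days after vaccination". In that case the laboratory tells the investigator, who is to "arrange for an extra visit for collection of a new nasopharyngeal sample for control of bacterial presence". VI.3.10 uses the same trigger: "In case the nasopharyngeal aspirate contains detectable vaccine strain bacteria on day 28 the laboratory contacts the clinical investigator or delegate". Neither place says what happens to the result of the new sample. SAP 1.4 does not carry the exception over.

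**The concern.** The strain is a live, genetically modified organism, given here at up to 10^9 cfu. Section III.3 relies on continued sampling, next to a statement that chronic carriage is not expected. The participant for whom that reliance matters most is one who is culture-positive at Day 28 and again at Visit 8'. For that person the plan does not say that the investigator is told, and it schedules no later culture to show whether carriage has ended.

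What is at stake is a safety assurance that the stated schedule and disclosure rule do not deliver. Clinical follow-up or advice that an investigator might offer a persistent carrier depends on knowing the result.

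**Working it through.** The plan gives no figure to reproduce on this point. The check sets the sections side by side and adds one interval.

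**1. Promise against schedule.** III.3 runs to the end of the study. The synopsis, flow chart and XII.4 all stop culture at Visit 8 (Day 28, window -1 to +7, so Day 27 to 35), or at Visit 8' (Day 45, window -5 to +10, so Day 40 to 55). The SAP adds Visit 10 in a 12-month follow-up of Groups 1 to 3. It names that visit for serum antibodies, nasopharyngeal IgA and haematology, and plans no culture there.

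**2. Following one participant through the rules.**
- Positive at Visit 8: exception 1 applies, the investigator is told, and Visit 8' is arranged.
- Positive at Visit 8': exception 1 does not name this sample and VI.3.10 gives no step for it, so the general hold applies. Exception 2 in II.3 concerns emergency breaking of the treatment code, not culture results.
- Visit 9: an aspirate is taken, but not for culture.

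**3. Time from the last culture to Visit 9.** Visit 9 is at 6±1 months. With the SAP convention of 30.4375 days per month:
- earliest: 5 × 30.4375 = Day 152
- latest: 7 × 30.4375 = Day 213
- shortest gap from Visit 8': 152 - 55 = 97 days
- longest gap from Visit 8': 213 - 40 = 173 days
- nominal gap: 6 × 30.4375 - 45 = about 138 days

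**4. Text that might close the gap.**
- Exception 1 gives a purpose for the extra sample: to check whether bacteria are still present. This suggests the result was meant to be used.
- Flow-chart note (i) is attached to the Visit 8' cell as well as the Visit 8 cell: "If positive culture after 4 weeks a new nasopharyngeal sample should be collected 2-4 weeks later for culture". It could be read to cover a positive Visit 8'. It names nobody to be informed, and no later culture visit exists. The matching footnote in XII.4 is tied to Day 28 (±1).
- XI.4 has the principal investigator or delegate evaluate laboratory abnormalities, and the flow chart lists the culture among the safety laboratory tests. This is a general rule; the hold in II.3 is specific to culture results.

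Each of the three points towards use of the result. None lifts the hold.

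**5. Endpoints and numbers.** The colonization objective (IV.2) covers 28 days, so no endpoint depends on later cultures. The documents give no Day-45 carriage rate. The first-in-man trial, as summarised in III.2, detected colonization between Days 4 and 28 at doses up to 10^7 cfu. It does not cover the 10^8 and 10^9 cfu doses used here. No count of affected participants can be derived.

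**The case against.** The case on the other side is reasonable. III.3 is background narrative, and the sections that govern conduct agree with one another. Section IV.1 treats the 28 days as the colonization period, and III.3 says that chronic carriage has not been reported. One conditional recall is a defensible design. The risk is argued to be low: III.3 cites a Biosafety level 1 classification, no cross-contamination in the previous trial, and transmission judged highly unlikely. Exclusion criterion 23 keeps out people in frequent contact with infants, and adverse events are reviewed at Visit 9.

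On notification, the hold exists to protect the blind, and that reason is largely spent once a Day-28 positive has been disclosed. It is also odd to have an investigator arrange a check and never see its result. The Laboratory analytical plan, to which XII.4 defers for detail, is not among the documents and may supply the step.

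Most of this stands, and it limits the weight of the point. It does not remove it. Site and laboratory staff who follow II.3 and SAP 1.4 as written would hold back a positive Visit 8' culture. Exclusion 23 is applied at entry, and the antibiotic provision in III.3 concerns accidental transmission to other people, not persistent carriage in a participant.

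**Conclusion.** The point holds as a gap in safety follow-up and should be corrected. III.3 claims more than the schedule delivers. For a participant positive at Visit 8', the plan states neither notification of the investigator nor a later culture, over the 97 to 173 days to Visit 9. This assumes that the visit windows are kept and that no unseen document adds a reporting step.

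Stronger readings are tempting, but the documents do not support them:
- *That the investigator is certain never to be told.* The purpose wording in exception 1, note (i) and XI.4 point the other way. The finding is that no route is stated.
- *That a positive result would be held for most of a year.* This needs the literal reading of the hold and a firm calendar. The protocol plans the last visit for September 2016 and the SAP for February 2017, while SAP 1.4 ties unblinding to lock of the 6-month data. No reliable duration follows.
- *That carriage goes unmonitored in everyone after Visit 8.* Most of those without a Visit 8' would be participants with a negative Day-28 culture. Their interval to Visit 9 is not undocumented carriage.
- *That the colonization results are compromised.* The objective ends at 28 days.

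The number of participants concerned is unknown and may be zero. The differing recall intervals (2-3 weeks in the synopsis and XII.4, 2-4 weeks in flow-chart note (i)) are a clerical matter and form no part of the case.

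**What to change.** (a) Extend exception 1 in II.3, and the matching text in VI.3.10, to any positive culture at Visit 8' or later, and carry the exception into SAP 1.4. The cost is a text change. No new unblinding arises: participants who reach Visit 8' have already been disclosed to the investigator as Day-28 positive, and Group 4 is open-label.

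(b) For participants whose Visit 8' culture is positive or missing, also culture the Visit 9 aspirate that is already collected, and mark this in the flow chart and XII.4. The cost is one extra plating per participant concerned, under the existing handling limits: catheter tip into enrichment medium within 1 hour, and delivery to the laboratory within 4 hours. No extra visit or aspiration is needed. The result shows whether carriage has ended by Visit 9; it does not date clearance.

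(c) Reword III.3 to state the actual culture schedule: Visits 3 to 8, Visit 8' if Day 28 is positive, Visit 9 under the rule in (b), and none at the SAP's Visit 10. The rewording is needed even with (b), because a missing Day-28 culture does not trigger Visit 8' and is not covered by this fix.

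The recall interval can be made consistent in the same edit.
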